5.2.2. Vital Signs

Vital sign measurements will be taken after the patient has been resting for at least 5 minutes, and will include systolic and diastolic blood pressure (BP) (millimeters of mercury [mmHg]), pulse oximetry, heart rate (beats/minute), respiratory rate (breaths/minute), and oral or tympanic temperature (degrees Celsius [°C] or degrees Fahrenheit [°F]).

5.2.3. Laboratory Assessments

Laboratory assessments are defined in section 11.4 of the protocol. Laboratory values will be graded according to the National Cancer Institute CTCAE version 4.03 or higher. Parameters which are not present in the CTCAE document will not be graded.

Samples collected at Screening may be tested at either a local or central laboratory. If local laboratory tests are used for LDH, platelet count, hemoglobin, and serum creatinine, duplicate samples will be collected for central laboratory testing to ensure baseline and postbaseline measurements for analyses are resulted from the central laboratory. In the event of duplicate samples from local and central laboratories (for any time point), central laboratory results will be used for analysis. Local laboratory results will only be used for analysis if no central laboratory results are available. Although local laboratory results may be used to expedite assessment of eligibility, the final determination of these Inclusion Criteria will be based on the central laboratory results. However, evaluation of Inclusion Criteria 2a and 2b may be based on local laboratory results within 28 days prior to the start of the Screening Period or laboratory results obtained during the Screening Period from a local or central laboratory.

It has been observed in other studies that up to 1% of central laboratory chemistry samples undergo in vitro erythrocyte lysis referred to as table top hemolysis (TTH) caused by sample mishandling. Due to the artefactual increase in LDH in samples affected by TTH, the potassium, ALT, AST, magnesium, phosphorous, and LDH values in samples affected by TTH will not be used in the analysis of any efficacy or safety endpoints. TTH samples from the central lab will be defined as having serum potassium ≥ 6 mmol/L and LDH $\geq 2x$ ULN, and will be excluded from analyses as described above.

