8. STUDY POPULATION

A total of approximately 55 patients with documented aHUS will be enrolled and assigned to treatment with ALXN1210 at approximately 200 investigative sites globally. The study will enroll at least 6 and up to 10 adolescent (12 to < 18 years of age at Screening) patients and at least 10 and up to 25 patients with prior kidney transplants. A minimum of 30 patients who meet all laboratory criteria for TMA (platelet count of < 150,000 per microliter, LDH $\geq 1.5 \times$ upper limit of normal (ULN), hemoglobin \leq lower limit of normal (LLN), and serum creatinine level \geq ULN) as determined by the central laboratory at Day 1, will be enrolled.

Individuals who do not satisfy the criteria for participation in this study (screen failure) may be rescreened based on discussion and agreement between the Investigator and the Medical Monitor. Patients may be rescreened a maximum of 2 times.

Prospective approval of protocol deviations to recruitment and enrollment criteria, also known as protocol waivers or exemptions, is not permitted.

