8.1. Inclusion Criteria

Patients are eligible for enrollment in the study only if they meet all of the following criteria and none of the exclusion criteria:

1. Male or female patients ≥ 12 years of age and weighing ≥ 40 kg at the time of consent.
2. Evidence of TMA, including thrombocytopenia, evidence of hemolysis, and kidney injury, based on the following laboratory findings:
 - a. Platelet count < 150,000 per microliter (μL) during the Screening Period or within 28 days prior to the start of the Screening Period, **and**
 - b. LDH $\geq 1.5 \times$ upper limit of normal (ULN) during the Screening Period or within 28 days prior to the start of the Screening Period, and hemoglobin \leq lower limit of normal (LLN) for age and gender during the Screening Period or within 28 days prior to the start of the Screening Period, **and**
 - c. Serum creatinine level \geq ULN during the Screening Period in adults (≥ 18 years of age), or $\geq 97.5^{\text{th}}$ percentile for age ([Appendix A](#)) at Screening in adolescents (12 to < 18 years of age) (patients who require dialysis for acute kidney injury are also eligible).
3. Among patients with a kidney transplant:
 - a. Known history of aHUS prior to current kidney transplant, **or**
 - b. No known history of aHUS, and persistent evidence of TMA at least 4 days after modifying the immunosuppressive regimen (eg, suspending or reducing the dose) of calcineurin inhibitor ([CNI]; eg, cyclosporine, tacrolimus) or mammalian target of rapamycin inhibitor ([mTORi]; eg, sirolimus, everolimus).
4. Among patients with onset of TMA postpartum, persistent evidence of TMA for > 3 days after the day of childbirth.
5. To reduce the risk of meningococcal infection (*Neisseria meningitidis*), all patients must be vaccinated against meningococcal infections within 3 years prior to, or at the time of,

initiating study drug. Patients who receive a meningococcal vaccine less than 2 weeks before initiating ALXN1210 treatment must receive treatment with appropriate prophylactic antibiotics until 2 weeks after vaccination. Patients who have not been vaccinated prior to initiating ALXN1210 treatment should receive prophylactic antibiotics prior to and for at least 2 weeks after meningococcal vaccination.

6. Patients < 18 years of age must have been vaccinated against *Haemophilus influenzae* type b (Hib) and *Streptococcus pneumoniae* according to national and local vaccination schedule guidelines.

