7. Female patients of childbearing potential and male patients with female partners of childbearing potential must follow protocol-specified guidance ([Section 9.10](#)) for avoiding pregnancy while on treatment and for 8 months after last dose of study drug.
8. Willing and able to give written informed consent and comply with the study visit schedule. For patients < 18 years of age, patient's legal guardian must be willing and able to give written informed consent and the patient must be willing to give written informed assent (if applicable as determined by the central or local Institutional Review Board [IRB]/ Institutional (or Independent) Ethics Committee [IEC]).

Evaluation of Inclusion Criteria 2a and 2b may be based on local laboratory results within 28 days prior to the start of the Screening Period or laboratory results obtained during the Screening Period from a local or central laboratory. If a local laboratory is used to define eligibility, additional samples will be collected during the Screening Period for LDH, platelet count, hemoglobin and serum creatinine and tested at the central laboratory. If patients are found to not meet the eligibility criteria for serum creatinine (Inclusion Criterion 2c) based on central laboratory results, they must not be enrolled into the study; if the subject has received the first dose of ALXN1210 the patient must be withdrawn from the study, and may be replaced. All analyses in this study will be based on results from the central laboratory. A central laboratory result for Inclusion Criterion 2c may not be available prior to first dose; results received after the first dose indicating that eligibility is not satisfied could lead to discontinuation and replacement of the patient.

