11.7. Adverse Event Management

An AE is any untoward medical occurrence in a patient administered a pharmaceutical product and which does not necessarily have a causal relationship with this treatment. An AE can therefore be any unfavorable or unintended sign (eg, an abnormal laboratory finding), symptom, or disease temporally associated with the use of a medicinal product, whether or not considered related to the medicinal product.

Situations in which an untoward medical occurrence did not occur (eg, hospitalization for elective surgery if planned before the start of the study, admissions for social reasons or convenience), and anticipated day-to-day fluctuations of pre-existing disease(s) or condition(s) present or detected at the start of the study that do not worsen are not AEs.

Lack of drug effect is not an AE in clinical studies, because the purpose of the clinical study is to establish drug effect.

A medication error (including intentional misuse, abuse, and overdose of the product) or use other than what is defined in the protocol is not considered an AE unless there is an untoward medical occurrence as a result of a medication error.

Cases of pregnancy that occur during maternal or paternal exposure to investigational product are to be reported within 24 hours of Investigator/site awareness. Data on fetal outcome and breastfeeding will be collected for regulatory reporting and safety evaluation.

Adverse events should be recorded from the time of signed consent. An AE reported after informed consent but before study drug administration will be considered a pretreatment AE.

Alexion has reporting standards for AEs that are to be followed as described in [Section 11.7.6](#) regardless of applicable regulatory requirements that may be less stringent.

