7.3.3. Other Safety

7.3.3.1. Analyses for Laboratory Tests

Observed values and changes from baseline in clinical chemistry, hematology, and urinalysis results will be summarized descriptively at baseline, and at each postbaseline time point. For laboratory results that can be classified as normal, low, or high based on normal range values, shifts from baseline in classification will be summarized for all study visits.

All data will be presented in listings, and a specific listing of abnormal results will be provided. For analysis purposes, laboratory results based upon standardized units will be used.

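### CTCAE laboratory grading is specified but feeds no planned output, and the low/normal/high shift table cannot show further worsening in patients already out of range at baseline

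*SAP*

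**What the plan says.** SAP 5.2.3 commits to a grade for each gradable laboratory value: "Laboratory values will be graded according to the National Cancer Institute CTCAE version 4.03 or higher". Parameters that CTCAE does not cover stay ungraded.

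SAP 7.3.3.1 lists the laboratory safety outputs:
- Continuous summaries at baseline and each visit: "Observed values and changes from baseline in clinical chemistry, hematology, and urinalysis results will be summarized descriptively".
- A three-class table (low, normal, high) in which "shifts from baseline in classification will be summarized for all study visits".
- Listings: "All data will be presented in listings, and a specific listing of abnormal results will be provided".

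Protocol 15.9.3 plans the same descriptive and shift summaries. None of these places mentions the grade.

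On entry, Protocol 8.1 (criterion 2c) asks for serum creatinine at or above "ULN during the Screening Period in adults", or at or above the 97.5th percentile for age in adolescents. Patients on dialysis for acute kidney injury are also eligible. For platelets, LDH and hemoglobin the window is wider: "Evaluation of Inclusion Criteria 2a and 2b may be based on local laboratory results within 28 days prior to the start of the Screening Period". Protocol 8 adds a quota: at least 30 patients meeting all four laboratory criteria for TMA, "as determined by the central laboratory at Day 1, will be enrolled".

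**The concern.** A definition that feeds no output is a loose end. Here it matters somewhat more, because the categorical table that is planned has little resolution in the disease-defining parameters. Someone who starts with low platelets or high creatinine is classed as unchanged whether the value is stable or much worse. Someone who normalizes and then relapses to below the starting value is also classed as unchanged from baseline.

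In a single-arm trial there is no control group against which to read averages, so a count of patients who got worse, and by how much, is a useful safety summary. If most patients improve, means and mean changes will say little about a minority who deteriorate. Grades would also help for analytes that are normal at entry: a rise to just above ULN and a rise to many times ULN both read as normal to high.

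**Working it through.** The plan gives no figure to reproduce on this point. The check sets the sections side by side, with one count.

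**1. Where the grade is used.** SAP 5.2.3 defines it. SAP 7.3.3.1 and Protocol 15.9.3 do not use it. SAP 7.3.2.4 tabulates CTCAE severity, but of adverse events, not of laboratory values.

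**2. Who is out of range at baseline.** SAP 9.4.2 sets baseline as the average of the pre-dose values, so the qualifying value and the baseline can differ.
- Creatinine: criterion 2c must be met in the Screening Period, so nearly all patients start high. The exceptions are values exactly at the limit and some dialysis patients, whose baseline is a later value taken at least 6 days after dialysis.
- Platelets, hemoglobin, LDH: the quota guarantees 30 of about 55 at Day 1, and 30/55 = 54.5%. The remaining 55 − 30 = 25 (25/55 = 45.5%) need not meet all four criteria. The documents do not say how many of those 25 are in range on any one parameter.

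**3. What the three-class table shows.** Take 150 (thousand per microliter, the documents' platelet threshold) as the lower limit. An upper limit of 400 is assumed and does not affect the result.

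| Baseline | Postbaseline | Class | Shift shown? |
|---|---|---|---|
| 100 | 20 | low to low | no |
| 160 | 20 | normal to low | yes |

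The table therefore misses worsening only in patients already out of range in the disease direction.

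**4. Which values reach the table.** Under SAP 9.4.5, one value is kept per analysis visit, the one closest to the scheduled day. A worse unscheduled value in the same window drops out of the by-visit tables and remains only in the listings.

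**5. What the other outputs add.**

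| Output | What it shows | What it does not show |
|---|---|---|
| Minimum and maximum (SAP 7) | extreme values at a visit | how many patients worsened, and from what baseline |
| CKD stage (SAP 7.2.2.5) | a worsened category for kidney function | worsening from baseline Stage 5, which includes dialysis (SAP 9.4.11); platelets, hemoglobin, LDH |
| Response components (SAP 7.2.2.3) | normalization, creatinine improvement | worse as distinct from not normalized |
| Hemoglobin response (SAP 7.2.2.7) | increase of at least 20 g/L | any decrease |
| Listings (SAP 7.3.3.1) | every value | a count or rate |
| Adverse events (Protocol 11.4, 11.7) | changes judged clinically significant | changes that do not alter medical care |

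On the last row, Protocol 11.7 also says "Lack of drug effect is not an AE in clinical studies", which leaves room not to report worsening of the disease itself.

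**6. Precedent in the SAP.** For ECGs, SAP 7.3.3.3.1 already plans a shift from baseline to the worst on-study result. Laboratory data have no counterpart.

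**The case against.** The strongest case against is that worsening is not lost from the report. Summaries of observed values and changes include minimum and maximum, so a platelet count of 20 would stand out. CKD stage has a worsened category with an exact confidence interval. Dialysis status is tabulated over time, including for patients not on dialysis at entry. Abnormal results have their own listing, which is readable with about 55 patients. Protocol 11.4 requires clinically significant changes to be recorded as adverse events, and these are graded and tabulated by severity. The four parameters are also efficacy variables and are analyzed at length.

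All of that stands, and it limits the point. It does not supply a count of patients who worsened in platelets, hemoglobin or LDH, and it gives the laboratory grade no use.

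A reader might go further and infer that, because entry requires abnormal values, worsening in these parameters cannot register as a shift at all. The documents do not support that. Platelets, LDH and hemoglobin may qualify on results up to 28 days before Screening, the baseline is an average, and up to 25 of about 55 patients need not meet all four criteria at Day 1. SAP 7.2.1.2 has a subgroup for patients who do. Anyone in range at baseline can show a shift. Nor is the three-class table the only categorical output built on laboratory data; that is true of the laboratory safety section, not of the whole SAP.

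It is also fair to object that the CTCAE cut-offs are not in the documents, so how finely the grades would separate baseline from worsening cannot be judged here.

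**Conclusion.** The point holds in a limited form. Laboratory grading is specified and unused, and the planned shift table cannot show further worsening in patients already out of range: nearly all for creatinine, and at least 30 of about 55 (55%) for each of platelets, hemoglobin and LDH.

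The 55% rests on three assumptions: that Day 1 status carries over to the averaged baseline, that the laboratory's lower limit for platelets matches the 150,000 threshold, and that few hemoglobin values sit exactly at the lower limit, where they meet the criterion but are in range. It is a planned minimum at Day 1, not an estimate of the true share.

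No primary or secondary result is affected. This is an inexpensive improvement to safety reporting, not an error that invalidates an analysis.

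**What to change.** In SAP 7.3.3.1, for parameters that CTCAE grades, add a table of baseline grade by worst postbaseline grade, using scheduled and unscheduled values. Report n (%) worsening by at least 1 grade and n (%) worsening to Grade 3 or higher, through 26 weeks and for the entire study.

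- Apply the exclusions the SAP already has: creatinine on dialysis (9.4.9), platelets and hemoglobin around transfusion (9.4.10), and samples flagged for table top hemolysis (5.2.3). Footnote how many values each rule removes, because severe deterioration can fall among them.
- For patients on dialysis at baseline, look for the worst creatinine grade only after the assessment that supplies their baseline. Count those with no baseline creatinine as not evaluable.
- Keep low/normal/high for ungraded parameters. If LDH is ungraded, use classes from the documents' own cut-offs: up to ULN, above ULN to below 1.5, 1.5 to below 2, and 2 or more times ULN.

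The cost is SAP wording and one or two extra tables from grades the SAP already says will be assigned, with no new data. The bare minimum would be to delete the grading sentence, but that would leave the gap in the shift table.

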5.2.4. Physical Examinations

A physical examination will include the following assessments: general appearance; skin; head, ear, eye, nose, and throat; neck; lymph nodes; chest; heart; abdominal cavity; limb; central nervous system; and musculoskeletal system. An abbreviated physical examination consists of a body system relevant examination based upon Investigator judgment and patient symptoms.

5.2.5. Electrocardiograms

For each patient, single 12-lead digital ECGs will be collected according to the Schedule of Assessments. Patients must be supine for approximately 5 to 10 minutes before ECG collection and remain supine but awake during ECG collection.

The Investigator or designee will be responsible for reviewing the ECG to assess whether the ECG is within normal limits and to determine the clinical significance of the results. These assessments will be indicated on the CRF. For any clinically significant abnormal ECG results, the Investigator must contact the Medical Monitor to discuss the patient's continued eligibility to participate in this protocol.

5.2.6. Immunogenicity

Blood samples will be collected to test for presence and titer of ADAs to ALXN1210 in serum prior to study drug administration as indicated in the Schedule of Assessments.

5.2.7. Other Safety Events of Special Interest

Meningococcal infections will be considered as AEs of special interest.

6. DATA SETS ANALYZED (STUDY POPULATIONS)

6.1. Full Analysis Set

The full analysis set (FAS) will be used for the primary analysis of efficacy. The FAS will be based on a modified intent to treat (mITT) approach where patients that were enrolled and treated based on verification of inclusion and exclusion criteria through local laboratory results and the assumption that all inclusion and exclusion criteria were satisfied will be excluded from the FAS if it is later shown that certain inclusion and exclusion criteria were in fact not satisfied once all Screening laboratory results are available. Based on the above, the FAS will include all patients who receive at least 1 dose of ALXN1210, have at least 1 postbaseline efficacy assessment, and meet all of the following criteria:

- Patients who satisfy Inclusion Criterion number 2c
- Patients who satisfy Exclusion Criterion number 1
- Patients who satisfy Exclusion Criterion number 2

See protocol sections 8.1 and 8.2 for the full list and description of the inclusion and exclusion criteria.

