5. INTRODUCTION

Atypical hemolytic uremic syndrome (aHUS) is a complement-mediated thrombotic microangiopathy (TMA), most often caused by mutations in genes encoding proteins involved in the alternative pathway of complement (APC) or by autoantibodies against APC regulatory proteins (Noris, 2010). Patients with aHUS are at risk for life-threatening manifestations of disease resulting from endothelial damage, including thrombocytopenia, intravascular hemolysis, acute renal failure, and extra-renal tissue damage. Importantly, approximately 20% of patients experience extra-renal manifestations of disease, including central nervous system, cardiac, gastrointestinal, distal extremity, and severe systemic organ involvement (Loirat, 2011; Brodsky, 2015). Before the availability of eculizumab, mortality rates among patients with aHUS were as high as 15% during the acute progressing phase of the disease (Noris, 2010; Sellier-Leclerc, 2007). Up to 50% of patients progressed to end-stage kidney disease (ESKD), often within a year of disease onset, and required dialysis or kidney transplant to sustain life.

Chronic, uncontrolled terminal complement activation, specifically, activation of complement component 5 (C5) and dysregulation of complement activity, is central to the pathogenesis of aHUS and the devastating manifestations of this disease. As a result, the targeted blockade of C5, with selective inhibition of generation of C5a and C5b-9, represents an important therapeutic mechanism of treatment.

Eculizumab (Soliris[®]) is the standard of care for aHUS patients. Eculizumab is a humanized monoclonal antibody that specifically binds to the complement protein C5 with high affinity. Eculizumab has no known off-target interactions with other proteins in vitro or in vivo. In addition, eculizumab is predicted to be effectorless, having no detectable binding to complement C1q or most Fcγ receptors (FcγR I, IIb/c IIIa, IIIb) and more than 10-fold weaker binding than an IgG1 isotype to FcγR IIa. Upon binding to the complement protein C5, eculizumab blocks cleavage to C5a and C5b by C5 convertase; which prevents generation of the terminal complement complex C5b-9. These attributes underlie the established safety and therapeutic efficacy profile of eculizumab as demonstrated in the 3 pivotal Phase 2 clinical studies (C10-003, C10-004, and C08-002A/B) and supported by subsequent postmarketing experiences.

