15.3. Analysis Sets

Efficacy analyses will be performed on the FAS. The analysis of the FAS will be the primary analysis.

The FAS will be based on a mITT approach where patients that were enrolled and treated based on verification of inclusion and exclusion criteria through local laboratory results and the assumption that all inclusion and exclusion criteria were satisfied will be excluded from the FAS if it is later shown that certain of the inclusion and exclusion criteria were in fact not satisfied once all Screening laboratory results are available. Based on the above, the FAS will include all patients who receive at least 1 dose of ALXN1210, have at least 1 postbaseline efficacy assessment, and meet all of the following criteria:

- Patients who satisfy Inclusion Criterion number 2c
- Patients who satisfy Exclusion Criterion number 1
- Patients who satisfy Exclusion Criterion number 2

The FAS will be determined prior to database lock and prior to the database snapshot for the analysis performed at the end of the 26-week Initial Evaluation Period.

Safety analyses will be performed on the Safety Set, defined for all patients who receive at least 1 dose of study drug.

Pharmacokinetic and PD analyses will be performed on all patients who receive at least 1 dose of study drug and who have evaluable PK and PD data.

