6.2. Per Protocol Set

The per protocol set (PPS) will consist of FAS patients who meet all of the following criteria:

- Received 100% of the planned number of infusions during the 26 week Initial Evaluation Period
- Did not take any prohibited medications or undergo any prohibited procedures (see protocol section 9.7)
- Satisfied inclusion criteria 2 and 8, and exclusion criteria 3, 7, 10, 11, 12, 13, 15, 16, 17, 18, 21, 22 and 26

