6.3. Safety Set

Safety analyses will be performed on the Safety Set defined as all patients who receive at least 1 dose of study drug.

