7.2.1. Primary Analysis

The primary efficacy endpoint is Complete TMA Response during the 26-week Initial Evaluation Period. The primary analysis will consist in estimating the proportion of complete TMA responders among ALXN1210 treated patients. This will be performed by calculating the point estimate and a 2-sided 95% confidence interval (CI) for the proportion of complete TMA responders in ALXN1210 treated patients, where the numerator will be the number of patients achieving complete TMA response during the 26-week Initial Evaluation Period and the denominator will be the number of patients in the FAS. The CI will be based on the asymptotic Gaussian approximation method with a continuity correction.

The criteria for Complete TMA response are presented in [Section 5.1.1](#). Patients must meet all Complete TMA Response criteria at 2 separate assessments obtained at least 4 weeks (28 days) apart, and any measurement in between. To be considered a responder during the 26-week Initial Evaluation Period, the latest time point a patient can first meet the response criteria is 28 days before the Day 183 assessment.

Formal statistical comparison analyses are not planned for this estimation study. Results from ALXN1210 treated patients will be evaluated in the context of results observed in patients treated with eculizumab in prospective eculizumab studies.

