7.2.1.1. Handling of Dropouts or Missing Data

For evaluation of Complete TMA Response during the 26-week Initial Evaluation Period (primary endpoint), patients missing an efficacy assessment that is part of the definition of Complete TMA Response while still on-study, will have their last observation carried forward (LOCF). For patients who will have discontinued from the study prior to Week 26, their data up to the time of discontinuation will be used to assess Complete TMA Response. A confirmatory result cannot be from an assessment that was carried forward from the initial assessment when all Complete TMA Response criteria were met.

For laboratory data, in the event of duplicate samples from local and central laboratories (for any time point), central laboratory results will be used for analysis.

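### The full analysis set drops eligible treated patients who have no postbaseline efficacy assessment, so they leave the primary denominator instead of counting as non-responders

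*SAP*

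**What the plan says.** SAP 7.2.1 names the target: "The primary analysis will consist in estimating the proportion of complete TMA responders among ALXN1210 treated patients". It then fixes the calculation: "the denominator will be the number of patients in the FAS".

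FAS membership under SAP 6.1 needs three things: at least one dose, eligibility on Inclusion Criterion 2c and Exclusion Criteria 1 and 2, and that the patient "have at least 1 postbaseline efficacy assessment". Protocol 15.3 has the same rule ("have at least 1 postbaseline efficacy assessment, and meet all of the following criteria"), and the efficacy part of the Protocol Synopsis repeats it.

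The reason given for this modified intent-to-treat set concerns eligibility only: some patients are dosed on local laboratory results and later prove ineligible once all Screening results are in. Protocol 8.3.4 gives the same purpose for replacing patients. No reason is given for the postbaseline requirement.

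For patients who leave before Week 26, SAP 7.2.1.1 says "their data up to the time of discontinuation will be used to assess Complete TMA Response", and Protocol 15.12.1 has the same rule. By contrast, SAP 6.3 has a "Safety Set defined as all patients who receive at least 1 dose of study drug", with no postbaseline condition.

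**The concern.** Exclusions for Inclusion 2c and Exclusions 1 and 2 rest on facts fixed before treatment. The postbaseline requirement depends on what happens after the first dose. Day 1 laboratory samples are taken before dosing (Protocol 11.4 and Table 1), and the next scheduled visit is Day 8, with a window of 2 days either side. A patient who is dosed and then dies, withdraws consent or is withdrawn without any postbaseline efficacy assessment is left out of the denominator.

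Some of these patients may be treatment failures. Protocol 9.7, for example, withdraws from the study any patient who receives another complement inhibitor or plasma exchange or infusion after the first dose.

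In a single-arm study the denominator is part of the estimate, and no control arm is subject to the same exclusion. The rate is also to be read in the context of eculizumab studies (Protocol 7.2, SAP 7.2.1), so it should describe the population that the plan names.

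**Working it through.** **Can any other provision put these patients back?**

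- The missing-data rules carry the last observation forward while a patient is on study and use data up to discontinuation after that. Both act on patients already in the FAS.
- The only alternative set for the primary endpoint is the per protocol set (SAP 7.2.1.5), and SAP 6.2 reads "The per protocol set (PPS) will consist of FAS patients who meet all of the following criteria". A subset of the FAS cannot restore anyone.
- The Safety Set has the wider population, but no efficacy analysis is planned on it.
- Patients who terminate early are not replaced (Protocol 8.3.1).

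**Direction.** Complete TMA Response needs all criteria met at two assessments at least 28 days apart (SAP 5.1.1). A patient with no postbaseline assessment cannot meet this, so removal lowers the denominator and leaves the numerator unchanged.

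**The plan's own precision figure (SAP 9.3).** Inputs: 65% response, 50 evaluable patients, 95% normal-approximation interval with continuity correction.

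- Half-width = 1.96 × √(p(1 − p)/n) + 1/(2n)
- n = 50: 1.96 × √(0.65 × 0.35/50) + 1/100 = 0.132 + 0.010 = 14.2 points, against a stated figure of about 15. This agrees loosely and is not disputed.
- n = 55: 0.126 + 0.009 = 13.5 points.
- Planned size: 50/0.9 = 55.6, rounded up to 56, against 55 stated; 55 × 0.9 = 49.5. Also not disputed.

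**Size of the shift.** Assumptions: N = 55 treated patients satisfy 2c and Exclusions 1 and 2; r = 36 respond; k have no postbaseline efficacy assessment. The documents give no value for k, so a range is shown.

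- All eligible treated patients: 36/55 = 65.5% (95% CI 52.0 to 78.9)
- Planned FAS: r/(N − k)
- Rise: r/(N − k) − r/N = rk/(N(N − k)); for k = 1, 36/(55 × 54) = 1.2 points

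| k | Planned FAS | 95% CI | Rise (points) |
|---|---|---|---|
| 1 | 36/54 = 66.7% | 53.2 to 80.2 | 1.2 |
| 2 | 36/53 = 67.9% | 54.4 to 81.4 | 2.5 |
| 3 | 36/52 = 69.2% | 55.7 to 82.7 | 3.8 |
| 4 | 36/51 = 70.6% | 57.1 to 84.1 | 5.1 |
| 5 | 36/50 = 72.0% | 58.6 to 85.4 | 6.5 |

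At a lower rate, 32/55 = 58.2%, the rise is 1.1 points for k = 1 and 4.6 for k = 4.

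**Who is caught.** Neither document defines a postbaseline efficacy assessment. It is unclear whether one component is enough. It is also unclear whether a result on Days 2 to 4 counts, because the midpoint rule in SAP 9.4.4 starts the Day 8 window at Day 5. The FAS is settled before the snapshot (Protocol 15.3), but the study is open label, so outcomes can be known when these questions are decided.

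**The case against.** The strongest reply is that very few patients can be affected. A reader might infer that every patient who dies or leaves in the first week drops out of the denominator, and the documents do not support that. Early termination assessments are done as soon as possible and include chemistry and hematology (Protocol 8.3.1, Tables 1 and 3). Unscheduled tests are allowed (Protocol 7.3), and local results are used when no central result exists (SAP 5.2.3). Dialysis requirement status is itself a listed efficacy assessment (Protocol 10.2), so a laboratory result may not be needed. An early leaver with any qualifying result stays in the FAS and already counts as a non-responder. Others who leave early because Screening results show them ineligible are excluded under either rule. This narrows the point to patients with no qualifying post-dose result, and it stands.

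A reader might also size the problem from Protocol section 5, which says "mortality rates among patients with aHUS were as high as 15% during the acute progressing phase of the disease". That figure is an upper bound from before eculizumab was available, over the acute phase. It is not a first-week rate or a rate under C5 inhibition, and it says nothing about k.

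The plan's whole dropout allowance through Day 183 is 10%, about 5 of 55, so k = 4 would put most of it in the first days. There is no hypothesis test or success threshold (SAP 7.2.1.4), so a shift of 1 or 2 points changes no planned decision. Exclusions will be listed (Protocol 15.1) and disposition covers all patients, so a careful reader could rebuild the wider denominator. All of this limits the importance. It does not explain why the primary estimate should differ from its stated target, and a denominator that readers must rebuild is not a planned analysis.

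**Conclusion.** The point holds in a narrow form. Eligible treated patients with no postbaseline efficacy assessment leave the primary denominator, although the stated target is the response rate among treated patients. The exclusion depends on events after treatment, can only raise the rate, and is offset by nothing else in the plan.

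The rise is about 1.2 points for the first such patient and 5.1 points for four, under the assumption of 36 responders among 55 eligible treated patients. The half-width is about 13.5 points, but the interval does not reflect a shift that runs in one direction only. The number affected is not given, is probably small, and may be zero, in which case the result does not change. The documents do not support reading this as a large bias or as the loss of all early deaths. It is a minor flaw that is worth repairing because the repair is cheap.

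**What to change.** 1. Delete the postbaseline-assessment condition in the Protocol Synopsis, Protocol 15.3 and SAP 6.1. The FAS is then all patients who received at least one dose, satisfy Inclusion 2c, and are not excluded by Exclusions 1 or 2 on Screening data.
2. State in Protocol 15.12.1 and SAP 7.2.1.1 that FAS patients without postbaseline data are non-responders for the primary endpoint.
3. State in SAP 7.2.2.2 how these patients are censored in the Kaplan-Meier analysis, which now censors non-responders at last visit or study discontinuation.

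If the sponsor keeps the clause for the primary analysis, the minimum is to add this wider denominator as a sensitivity analysis of the primary endpoint in SAP 7.2.1.5 and to define what counts as a postbaseline efficacy assessment.

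The cost is a few sentences and no new data. Change-from-baseline summaries by visit are unaffected, since these patients have no postbaseline values. The one downside is that the reported rate may be slightly lower.
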